10.2 Statistical methods

The analyses will be done in the intention-to-treat (ITT) population defined as all randomised participants for whom there is consent for the use of data. We will perform the primary analyses adjusted for the stratification variables [45] and challenge the primary result in analyses adjusted for important baseline risk factors (co-morbidities, higher SMS score, and focus of infection (other foci vs. urinary tract infection)[43, 46] and use of corticosteroids, which may reduce the time in ICU and thus the time exposed to the protocol [47]) and analyses of subgroups (Table 2) and the per-protocol population being the ITT population except those having one or more major protocol violations as defined below (Table 3). If there is more than 5% missing data for outcomes and/or covariates, we will impute the missing data using multiple imputations as described below (10.2.4).

All analyses will be 2-tailed and we will use Fisher's exact test for unadjusted comparisons of dichotomized outcomes (mortality at 90-days and 1-year, SAEs and SARs) and logistic regressions for adjusted analyses of these outcomes. The remaining secondary outcomes are continuous measures; we expect that these are highly skewed (non-normally distribution), because of inflation of specific values such as zero for days alive outside hospital for all patients who die while at the ICU. We will use statistical methods that can accommodate this type of data; the precise models will be specified in the detailed statistical plan.

Several of the secondary outcome measures are composite; we will also analyse each component of these outcomes as recommended [42]; the precise models will be specified in the detailed statistical plan.

Table 2. Heterogeneity of the intervention effects on the primary outcome will be analysed in the following subgroups based on baseline characteristics

Subgroup	Definition	Expected direction of	Statistical test
		the interaction	
Participants who are mechanically ventilated	Invasive mechanically ventilated (yes/no)	Larger effect of fluid restriction in mechanically ventilated participants	Test of interaction in the adjusted analysis described above; P- value 0.01

The CLASSIC trial protocol Page 32/82

Participants with	KDIGO (creatinine)	Larger effect of fluid	Test of interaction in
severe acute kidney	criteria of 2 or above	restriction in acute	the adjusted analysis
injury	[41] (yes/no)	kidney injury	described above; P-
			value 0.01

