A systematic review from 2016 by Vincent JL et al., which included 34 observational sepsis studies, showed that decrease in lactate concentration over time was consistently associated with lower mortality rates in all subgroups of patients (3). Hyperlactatemia is in clinical practice often thought to indicate that the human body is unable to uphold aerobic metabolism, due to tissue hypoxia and/or a deranged micro-circulation. This is often taken as an indication that a sufficient amount of resuscitation fluid has not yet been given to the patient. However, there are many other causes for hyperlactatemia, such as increased glycolysis, decreased clearance, and adrenergic stress response (4, 5).

In a Dutch multicenter randomized controlled trial from 2010 lactate-guided therapy in hyperlactatemia (albeit from various causes) reduced mortality, but interestingly the lactate levels did not differ significantly between the groups (6).

The current paradigm states that treatment with fluids decreases elevated concentrations of plasma lactate. Therefore, it is somewhat surprising that the post-hoc analysis of the Conservative versus Liberal Approach to fluid therapy of Septic Shock in Intensive Care (CLASSIC) feasibility trial (7)

The CLASSIC trial protocol Page 72/82

¹ Perioperative Medicine & Intensive Care, Karolinska University Hospital Huddinge, Sweden

² Department of Intensive Care, Rigshospitalet, University of Copenhagen, Copenhagen, Denmark.

³ Department of Anesthesia and Intensive care Medicine, Charles University Hospital Pilsen, Czech Republic

⁴ Department of Clinical Science and Education, Södersjukhuset, Karolinska Institutet, Stockholm, Sweden

showed no significant differences in plasma lactate levels between the two treatment groups even though there was >1 L difference in received fluids between the groups. The trial itself was not powered to investigate this outcome, but the finding is worth investigating in the main study.

Trial hypotheses and outcomes

The objective of this sub-study of the CLASSIC-trial is to use the randomization to either restrictive or standard fluid therapy to study temporal changes of lactate and time to normalization in patients with septic shock.

Research questions:

- 1. Does the lactate values differ between the two intervention groups in terms of
- a. Temporal changes in concentrations over time (based on all available plasma lactate analyses during the first 72 hours).

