- b. Differences in delta-values (ΔLactate/h) over time (Calculated according to the method described under method & design).
- c. Differences in time to normalization (<2 mM/L) or discharge/death.
- 2. Same question(s) as above but comparing the cohort of patients with a higher baseline lactate (>4 mmol/L) in the two treatment arms.

Hypotheses:

- 1. Restrictive fluid therapy will neither significantly affect the delta-lactate nor time to normalization in patients treated for septic shock compared with standard (more liberal) fluid therapy
- 2. Patients in septic shock with a higher baseline lactate >4mmol/L will not decrease lactate levels faster with standard fluid therapy compared with restrictive fluid therapy. This is a sub-group analysis of 1).
- 3. A high baseline lactate and/or a low Δ Lactate/h is associated with a higher mortality irrespective of fluid treatment.

Outcome measure(s)

- 1. Primary outcomes are the differences in plasma lactate concentrations and Δ Lactate/h during the first 72 hours between the two treatment arms in the CLASSIC trial.
- 2. Secondary outcomes are the time to normalization of lactate, length of intensive care unit (ICU) stay and 90-day mortality in restrictive vs standard group of the CLASSIC trial.

The CLASSIC trial protocol Page 73/82

Method and design

All retrospective serial time-stamped point-of-care blood gas analyses from patients included in the CLASSIC trial will be collected and analyzed for the first 72 hours or until death or discharge from the ICU (depending on the availability from the centers).

Baseline characteristics (age, sex, body weight, pre-existing conditions and lab), daily fluid balance, urine output, treatment (mechanical ventilation, renal replacement therapy, vasopressors) and 90-day mortality data of included patients will be available from the CLASSIC trial database.

Normally distributed continuous data will be presented as mean +/- standard deviation and independent Student's t test will be used to compare means. Mann-Whitney U test will be used to compare mean ranks between groups if data shows non-normality assessed by the Shapiro-Wilk test. Such data will be presented as median (interquartile range). Data of categorical variables will be analyzed with Chi-square or Fisher's exact test as appropriate. A P-value of <0,05 will be considered as a statistically significant difference between groups for the primary outcomes.

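### Lactate sub-study: hypothesis 1 predicts no significant effect, and with only difference tests and no margin it is met by any non-significant result

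*Protocol*

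**What the plan says.** All of this is in Protocol Appendix 8, section 14.8.1.b; the SAP does not cover the sub-study.

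- **Research question 1** is put as a difference: "Does the lactate values differ between the two intervention groups in terms of". It lists concentration over time, change per hour, and time to normalisation. Question 2 asks the same in patients with baseline lactate above 4 mmol/L.
- **Hypothesis 1** is put as an absence of significance: "Restrictive fluid therapy will neither significantly affect the delta-lactate nor time to normalization in patients treated for septic shock".
- **Hypothesis 2** is directional and concerns the high-lactate subgroup: "Patients in septic shock with a higher baseline lactate >4mmol/L will not decrease lactate levels faster with standard fluid therapy" than with restriction.
- **Outcomes.** The primary outcomes are between-arm differences in lactate concentration and in ΔLactate/h over 72 hours. Time to normalisation is secondary.
- **Tests.** For normal data, "independent Student's t test will be used to compare means". Otherwise, "Mann-Whitney U test will be used to compare mean ranks between groups if data shows non-normality assessed by the Shapiro-Wilk test". Categorical data get chi-square or Fisher's exact test. A mixed model for repeated measures also compares the groups.
- **Decision rule.** "A P-value of <0,05 will be considered as a statistically significant difference between groups for the primary outcomes". No threshold is given for the secondary outcomes.
- **Sample size.** 784, the sum of patients already included at the contributing centres. No SD, effect size, power or margin is given. The planned summaries are mean with SD or median with IQR; confidence intervals are not mentioned.

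**The concern.** A difference test can support the statement that the arms differ. It cannot by itself support the statement that they do not, because non-significance also arises when a real difference is small relative to the noise. Hypothesis 1 is defined by significance, so scarcer or noisier data make it easier to satisfy. Data volume is uncertain here: blood gases are collected retrospectively as centres can supply them, and their number varies by patient and centre.

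The sub-study sets out to challenge the view that fluid lowers raised lactate. Its starting point is a post-hoc analysis of the feasibility trial that found no significant lactate difference, in a trial the authors say was not powered for it. A second non-significant P-value without an interval or margin would leave that question where it stood, while the hypothesis as written would count as met.

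**Working it through.** **1. The plan's own figure.** 130 (Sweden) + 604 (Zealand) + 50 (Pilsen) = 784. The figure reproduces exactly. It is a head count, so there is no power statement to check.

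**2. Inputs for the size of the problem.**
- Per arm: 784 / 2 = 392, from the 1:1 allocation in Protocol 3.2. This assumes an even split and usable data for everyone.
- Alpha 0.05, from the sub-study.
- Two-sided: assumed. The sub-study does not state sidedness; the main trial does (Protocol 10.2: "All analyses will be 2-tailed").
- One value per patient: assumed.
- Differences in SD units, because the sub-study gives no SD for lactate or ΔLactate/h.

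**3. Precision.** SE = sqrt(2/392) = 0.0714 SD. The 95% CI half-width is 1.96 × 0.0714 = 0.14 SD. An estimate that just misses significance therefore has an interval from about 0 to 0.28 SD.

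**4. Chance of a non-significant result when a difference exists.** Power ≈ Φ(d/SE − 1.96).

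| True difference d (SD) | d/SE | Power | Non-significant |
|---|---|---|---|
| 0.10 | 1.40 | 28.8% | 71% |
| 0.15 | 2.10 | 55.6% | 44% |
| 0.20 | 2.80 | 80.0% | 20% |
| 0.25 | 3.50 | 93.8% | 6% |
| 0.30 | 4.20 | 98.7% | 1% |

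**5. Subgroup with lactate above 4 mmol/L.** Its share is not given; 30% to 50% is assumed, or about 118 to 196 per arm. The difference detectable with 80% power is (1.960 + 0.842) × sqrt(2/n), which is 0.37 SD at 30% and 0.28 SD at 50%, against 0.20 SD in the full set.

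**6. What a margin would demand.** For hypothesis 1, an equivalence test with true difference zero and 80% power can use a margin no smaller than SE × (z + 1.282). That is 0.0714 × (1.645 + 1.282) = 0.21 SD when judged by the 90% CI, and 0.0714 × (1.960 + 1.282) = 0.23 SD by the 95% CI. For hypothesis 2, one-sided non-inferiority at 0.025 with 80% power uses the same formula as step 5, so the smallest margin is again 0.37 to 0.28 SD in the subgroup.

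**The case against.** Research question 1 and the primary outcomes are already framed as differences, and difference tests suit them. The hypotheses can be read as the investigators' expectation. The authors also qualify the feasibility trial's null lactate result by its lack of power, which suggests they would not treat a null as settled. This stands, and it confines the mismatch to the two hypothesis sentences and the missing interval criterion.

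Four stronger readings are tempting, and the documents do not support them.

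- A reader might infer that the sub-study plans to report non-significance as confirmation. No sentence says so.
- A reader might take both hypotheses as claims of equality. Hypothesis 2 says only that lactate "will not decrease lactate levels faster with standard fluid therapy compared with restrictive fluid therapy"; it is also compatible with a faster fall under restriction, so an equivalence rule would not fit it.
- A reader might apply the P<0.05 rule to everything in hypothesis 1. It is stated for the primary outcomes, and time to normalisation is secondary.
- A reader might put the uncertainty in mmol/L. With assumed SDs of 2, 3 and 4 mmol/L, 1.96 × SD × sqrt(2/392) gives half-widths of 0.28, 0.42 and 0.56 mmol/L. Those SDs are not in the documents, and the figures describe raw lactate at one time point, not the per-hour change that hypothesis 1 names. They are also small beside the 2 and 4 mmol/L cut-offs, so they do not show that a null result would be uninformative overall.

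**Conclusion.** The concern holds as a mismatch between hypothesis wording and analysis. Nothing in the sub-study separates a result that excludes a relevant difference from one that merely fails to detect it. With the full 784, non-significance would be weak evidence against true differences of about 0.10 to 0.15 SD (missed 71% and 44% of the time) and fairly good evidence against differences of 0.25 SD or more (missed 6% or less). In the high-lactate subgroup it says less.

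These figures rest on the assumptions in steps 2 and 5. Repeated values in the mixed model and missing blood gases would change them, in opposite directions. They do not measure time to normalisation, for which the sub-study names no time-to-event method.

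Severity is minor. This is an appendix sub-study outside the SAP, and the main trial's outcomes and inference do not depend on it.

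**What to change.** 1. Restate hypotheses 1 and 2 as two-sided questions that match research questions 1 and 2.
2. Report between-group estimates with 95% CIs: from the planned mixed model for lactate and ΔLactate/h, and from a suitable, separately specified analysis for time to normalisation, which the mixed model does not provide.
3. State that P of 0.05 or above is inconclusive, is reported with its interval, and is not evidence of no effect.
4. Allow a no-effect statement only if a margin is fixed before the data are opened: equivalence for hypothesis 1, one-sided non-inferiority for hypothesis 2. The documents give no basis for a margin, so the investigators would have to justify one on each outcome's own scale. If none can be agreed, or the data have already been opened, items 1 to 3 suffice.

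Items 1 and 3 are wording. Item 2 adds intervals to a planned model and one analysis for time to normalisation. No new patients or data are needed. Only item 4 requires real discussion, and it is optional.

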9.2.2 Timing

All variables are defined in Appendix 2.

Baseline variables:

- Sex
- Date of birth

The CLASSIC trial protocol Page 28/82

- Date of admission to hospital
- Date and time of admission to ICU
- From where was the participant admitted to ICU
 - o Emergency department or directly from the pre-hospital setting
 - Hospital ward
 - Operating or recovery room
 - Another ICU
- Focus of infection:
 - o Pneumonia
 - o Gastrointestinal infection
 - Urinary tract infection
 - Skin or soft tissue infection
 - Other
- Co-morbidities:
 - o Active hematologic cancer
 - History of metastatic carcinoma
 - History of ischemic heart disease or heart failure
 - History of chronic hypertension
 - o Chronic dialysis
- Blood values, interventions and vital parameters:
 - Participant weight
 - o Highest plasma lactate value within the last 3 hours of randomisation
 - Highest dose of noradrenaline within the last 3 hours of randomisation
 - o Volumes of IV fluid within the last 24 hours of randomisation
 - o Use of systemic corticosteroids in the last 24 hours of randomisation
 - Highest plasma creatinine value within the last 24 hours of randomisation
 - Use of acute renal replacement therapy in the last 3 days prior to randomisation
 - Habitual plasma creatinine value prior to current hospitalisation (mark estimated or measured)
- Values for the Simplified Mortality Score (SMS score)[43] at ICU admission not covered by the above:
 - Lowest measured systolic blood pressure in the last 24 hours prior to randomisation
 - Respiratory support within the last 24 hours of randomisation (support during surgery excluded)

Daily during ICU admission (day form):

- Fluid input and output
 - Total volume and specific type of IV isotonic crystalloids (isotonic saline and buffered solutions: Ringer's lactate, Ringer's acetate and PlasmaLyte™)
 - o Total volume of other IV fluids
 - Total volume of albumin
 - Total volume of fluids with medications
 - Total volume of fluids with nutrition
 - Total volume of blood products

The CLASSIC trial protocol Page 29/82

- Urinary output on this day (ml)
- Total volume of other losses on this day including drainage, aspirates, stools and bleeding
- Did a major protocol violation occur on this day?
- Use of infusion of vasopressor or inotrope on this day
- Use of systemic corticosteroids on this day
- Use of mechanical ventilation on this day
- Use of renal replacement therapy on this day
- Plasma concentration of creatinine

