Definition of baseline variables

- -Sex: the genotypic sex of the participant
- -Age: defined in inclusion criteria
- -Date of admission to hospital: the date of admission to the first hospital the participant was admitted to during the current hospital admission
- -Date and time of admission to the ICU (or high-dependency or step-up/step-down beds; see inclusion criteria): the date of admission to the first ICU the participant was admitted to during the current hospital admission
- -From where was the participant admitted to ICU
 - Emergency department or directly from the pre-hospital setting:
 Accident/Emergency/Casualty/Acute department in the same or another hospital or direct admission to the ICU by an ambulance service or similar

The CLASSIC trial protocol Page 46/82

- Hospital ward: Any location in the same or another hospital not covered in the other 3 categories
- Operating or recovery room: including surgical theatre, endoscopy and angiography suite and any recovery facilities observing patients following invasive procedures.
- Another ICU: either within the same or another hospital

Focus of infection (documented or suspected):

- o Pulmonary: e.g. pneumonia, or empyema
- Gastrointestinal infection: e.g. primary, secondary or tertiary peritonitis, abscess, cholangitis, cholecystitis, or invasive diarrhoeal disease
- Urinary tract infection: e.g. urinary tract infection, or pyelonephritis
- o Skin or soft tissue infection: e.g. cellulitis, phlegmon, erysipelas, or fasciitis
- Other: other infectious focus documented or suspected including meningitis, endocarditis, osteomyelitis, arthritis and bacteraemia
- -Co-morbidities, must have been present in the past medical history prior to ICU admission and are defined as follows:
 - o Active hematologic cancer: defined in the stratification variables
 - o History of metastatic carcinoma: defined in the stratification variables
 - History of ischemic heart disease or heart failure: previous myocardial infarction, invasive intervention for coronary artery disease, stable or unstable angina, NYHA class 3 or 4 or measured LVEF < 40%.

 - Chronic dialysis: use of renal replacement therapy at least once a week e.g. chronic haemodialysis or haemofiltration, peritoneal dialysis
- Blood values, interventions and vital parameters:
 - o Participant weight: measured or estimated in kg
 - Highest plasma lactate value within the last 3 hours of randomisation: in mmol/L

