ΔLactate/h is defined as (baseline lactate/baseline lactate – subsequent lactate) / baseline lactate x (100 / time interval(h)). Baseline lactate value is the lactate concentration at the time of randomization (from the electronic case report form). We will compare the groups using a mixed model for repeated measures to deal with missing values. Logistic multiple regression analysis for baseline lactate, ΔLactate/h and mortality adjusted for allocation treatment group and important risk factors (age, co-morbidities, severity of disease et cetera).

Centers will provide data in pseudonymized form. Data will be stored in an encrypted hard drive. Key for decryption and identification will be stored in a fire safe locked cabinet.

Sample size estimate

The Swedish centers have to date included 130 patients. Outside of Sweden the two hospital regions of Zealand, Denmark have included 604 patients and the University Hospital of Pilsen, Czech Republic, have included 50 patients. The estimated sample size will all together consist of 784 patients. The number of blood gas analyses will vary depending on patient and including center.

References:

- 1. Singer M et al (2016) The Third Inter- national Consensus definitions for sepsis and septic shock (Sepsis-3). JAMA 315(8):801–810
- 2. Evans L et al, Surviving sepsis campaign: international guidelines for management of sepsis and septic shock 2021, Intensive Care Medicine (2021) 47:1181–1247

The CLASSIC trial protocol Page 74/82

- 3. Vincent JL et al, The value of blood lactate kinetics in critically ill patients: a systematic review. Crit Care 2016:20;257
- 4. Hernandez G et al, The ten pitfalls of lactate clearance in sepsis, Intensive Care Medicine (2019) 45: 82-85
- 5. Garcia-Alvarez et al, Sepsis-associated hyperlactatemia, Critical Care 2014, 18:503
- 6. Jansen TC et al, LACTATE study group. Early lactate guide-therapy in intensive care unit patients: a multicenter, open-label, randomized controlled trial. Am J Respir Crit Care Med 2010;182:752-761.
- 7. Hjortrup et al, Effects of Fluid Restriction on measures of circulatory efficacy in adults with septic shock. Acta Anaesthesiol Scand 2017 Apr;61(4):390-398

The CLASSIC trial protocol Page 75/82

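### Lactate sub-study: the only printed formula for ΔLactate/h, one of two primary outcomes, does not give a percentage fall per hour, and the start of its time interval is not stated

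*Protocol*

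**What the plan says.** The sub-study compares "Lactate/h during the first 72 hours between the two treatment arms in the CLASSIC trial", together with lactate concentration, as its primary outcomes. Research question 1b refers the reader to the method section for the calculation. The only formula there is "ΔLactate/h is defined as (baseline lactate/baseline lactate – subsequent lactate) / baseline lactate x (100 / time interval(h", followed by the closing brackets. Neither the rest of the Protocol nor the SAP gives another definition.

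The next sentence reads "Baseline lactate value is the lactate concentration at the time of randomization (from the electronic case report form". The case report form item is described differently: Section 9.2.2 lists "Highest plasma lactate value within the last 3 hours of randomisation", and Appendix 2 repeats it with its unit. Section 9.2.2 lists no sampling time for that value.

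Hypothesis 3 shows the intended direction. It says that a high baseline lactate and/or a low value of Δ"Lactate/h is associated with a higher mortality irrespective of fluid treatment", so a higher score is meant to be better.

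**The concern.** An analyst who codes the outcome, or a reader who checks it, has only this formula to work from. As bracketed it is not a relative change per hour. Taken literally, it gives most falling lactate values a negative sign, gives unchanged lactate a value other than zero, and makes the score depend on sampling time even when nothing has changed. That would distort the reported level of a primary outcome, its pattern over 72 hours, and its use as a predictor in the mortality regression.

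A second, smaller gap is that the interval has no stated start. If hours are counted from randomisation while the baseline sample was drawn earlier, the rate is overstated, most of all for early samples.

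**Working it through.** Notation: B = baseline lactate, S = subsequent lactate (mmol/L), h = interval in hours. Section 4.1 requires lactate of 2 mmol/L or above for inclusion, so I take B ≥ 2. The other B, S and h values are illustrations. The sub-study prints no worked value to reproduce.

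**Three forms**

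- Intended, inferred from the name, the factor 100/h and hypotheses 2 and 3: (B - S)/B x 100/h.
- Printed, ordinary operator order: (B/B - S)/B x 100/h = (1 - S)/B x 100/h.
- Printed, numerator read as B/(B - S): [B/(B - S)]/B x 100/h = 100/[(B - S) x h].

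**Results at h = 6 (%/h on the intended scale)**

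| B to S | Intended | Ordinary order | Other grouping |
|---|---|---|---|
| 4 to 1 | +12.5 | 0 | +5.6 |
| 4 to 1.5 | +10.4 | -2.1 | +6.7 |
| 4 to 2 | +8.3 | -4.2 | +8.3 |
| 4 to 3 | +4.2 | -8.3 | +16.7 |
| 4 to 4 | 0 | -12.5 | undefined |
| 4 to 5 | -4.2 | -16.7 | -16.7 |

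Example, 4 to 2: intended (4 - 2)/4 x 100/6 = 8.3; ordinary order (1 - 2)/4 x 100/6 = -4.2; other grouping 100/(2 x 6) = 8.3.

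**Ordinary order.** The error is (1 - S)/B - (B - S)/B = 1/B - 1, times 100/h. It is zero only if B = 1, which the inclusion limit rules out. For B ≥ 2 it lies between -50/h and -100/h: -8.3 to -16.7 at 6 h, -2.1 to -4.2 at 24 h, and -0.7 to -1.4 at 72 h. The score is negative for every S above 1 mmol/L. A patient falling from 4 to 1.5 has normalised by the sub-study's own limit ("Differences in time to normalization (<2 mM/L) or discharge/death") but scores -2.1.

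**Other grouping.** It equals the intended form only when (B - S)² = B, which is why 4 to 2 agrees. Otherwise, larger falls score lower, contrary to hypothesis 3.

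**Contrast between two patients, 4 to 2 against 4 to 3, at 6 h**

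- Intended: 8.3 - 4.2 = +4.2 (from unrounded values)
- Ordinary order: -4.2 - (-8.3) = +4.2
- Other grouping: 8.3 - 16.7 = -8.3

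So at equal baseline and interval the error cancels under ordinary order, while the other grouping reverses the contrast.

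**Unequal sampling times, ordinary order, B = 4**

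- A fall to 2 at 6 h scores -4.2. A fall to 3 at 12 h scores (1 - 3)/4 x 100/12 = -4.2. The intended values are +8.3 and +2.1.
- Unchanged lactate at 24 h scores (1 - 4)/4 x 100/24 = -3.1, better than halving in 6 h at -4.2. The intended values are 0 and +8.3.
- Unchanged lactate scores -12.5 at 6 h and -6.25 at 12 h; the intended difference is 0.

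The plan says that "The number of blood gas analyses will vary depending on patient and including center". It does not say outright that intervals will differ, but that is to be expected when whatever blood gases exist are used.

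**Start of the interval, intended form, 4 to 2.** Compare hours from randomisation (h) with hours from a baseline sample drawn 3 h earlier (h + 3), the largest gap the case report form item allows:

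| Sample time after randomisation | 50/h | 50/(h + 3) | Excess |
|---|---|---|---|
| 6 h | 8.3 | 5.6 | 50% |
| 24 h | 2.08 | 1.85 | 12.5% |
| 72 h | 0.69 | 0.67 | 4% |

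**The case against.** The strongest reply is that this is a misplaced bracket. Moving one closing bracket gives (B/B - S/B) x 100/h, which is the percentage fall per hour, with every printed term kept in order. The name, the factor 100/h and the hypotheses leave little doubt about the meaning, and literal coding would probably be noticed at the first patient with stable lactate. This stands as an account of how the error arose and shows that the repair is small. It does not make the printed definition usable, and the figures above apply if it is followed literally.

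It can also be said that the primary outcome is a difference between arms and that, under ordinary operator order, the error depends only on a pre-randomisation value and on sampling time. That is right at equal sampling times, where randomisation balances the error in expectation. It does not protect the sign, the level or the time course. Nor does it protect a comparison in which sampling times differ by arm. The trial is open-label, and Section 6.1 names lactate among its criteria in the restrictive arm only, so this could happen; the documents do not show that it does. In the mortality regression, adjusting for baseline does not remove an error that varies with the interval. Even at a fixed interval, a linear baseline term would not fully absorb it, because 1/B is not linear in B.

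On the interval, randomisation is a natural reading of its start, and the 3 h gap is a maximum that matters little by 72 h. Both points are fair and keep this part secondary.

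**Conclusion.** The concern holds. The only definition of one of the sub-study's two primary outcomes is wrong as printed under either reading that keeps its brackets. At a baseline of 2 mmol/L or more, ordinary operator order shifts the score by -8.3 to -16.7 %/h at 6 h, shrinking to -0.7 to -1.4 at 72 h. The other grouping can reverse the contrast between arms. The unstated start of the interval adds at most 50% at 6 h and 4% at 72 h.

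These sizes assume literal use of the formula, the illustrative values shown and, for the interval, the maximum 3 h gap. The intended form is inferred, not printed. A fault in reading the PDF cannot be fully excluded, although the slashes and brackets are inline and explicit. Lactate concentration, time to normalisation and the main trial are not affected. This is a correction to the text, not a change of design.

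**What to change.** In Appendix 8, print ΔLactate/h = (baseline lactate - subsequent lactate) / baseline lactate x 100 / time interval (h), in percent per hour, with positive values meaning a fall. State that the interval runs from the time of the baseline sample to the time of the subsequent sample. If the baseline sampling time is not available, state that randomisation is time zero and that the baseline value may be up to 3 h older. Reword the description of baseline lactate to match the case report form item in Section 9.2.2 and Appendix 2.

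The cost is one corrected formula, one sentence on the interval and one on baseline. Later blood gases are already time-stamped; the baseline sampling time is extra data only if the interval is to run from it.
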